14.4 Pharmacokinetic Analyses

Subjects randomized to receive BMN 111 or placebo will undergo pharmacokinetic testing.

For subjects randomized to BMN 111, PK parameters generated over the course of the study will be evaluated and summarized with descriptive statistical measures (mean, standard deviation, CV%, min, median and max). Correlative analyses of some of the PK parameters with efficacy, safety and immunogenicity measures may be conducted.

14.5 Immunogenicity Analysis

Immunogenicity will be summarized as change from baseline as well as by study time point in subjects randomized to receive BMN 111 or placebo. Results will be summarized as incidence and titer for all cohorts. Additionally, immunogenicity may be assessed for correlations with measures of safety, PK, and efficacy.

14.6 Determination of Sample Size

Approximately 70 subjects age 0 to <60 months at study entry will participate in this study. No formal sample size calculations were performed. The number of subjects is considered appropriate to evaluate the safety and efficacy of BMN 111 in the target population.

14.7 Analysis Populations

14.7.1 Efficacy Population

All randomized subjects who receive at least one dose of double-blinded BMN 111 or placebo in this study.

14.7.2 Safety Population

All subjects who receive at least one dose of double-blinded BMN 111 or placebo in this study.

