
 • Area under the plasma concentration-time curve from 0 to the time of last measurable concentration (AUC_{0-t}) • Maximum plasma concentration (C_{max}) • Time to reach C_{max} (T_{max}) • Elimination half-life (t_{1/2}) • Apparent clearance of drug (CL/F) • Apparent volume of distribution based upon the terminal phase (Vz/F) 		
Drug accumulation after repeat-dose administration will also be evaluated. PK parameters at Week 13, 26, 39 and 52 will be compared to Day 1. The impact of immunogenicity (if present) on PK will also be evaluated.		
Bone metabolism and BMN 111 pharmacodynamic biomarkers: 
 • Changes in bone and collagen metabolism and BMN 111 activity will be assessed. 		
Clinical outcome assessments: 
 • Bayley-III • WeeFIM • CBCL • ITQOL 		
Exploratory: The following exploratory measurements will be assessed:		

 • Upper:lower body segment ratio • Imaging assessments (X-rays of the spine and lower extremities) • MRI to define skull and brain morphology (including dimensions of foramen magnum, ventricular and brain parenchymal dimensions) • Sleep study • Clinical photography (optional) 		
STATISTICAL METHODS:		
Sample Size Determination: Approximately 70 subjects age 0 to < 60 months at study entry will participate in this study. No formal sample size calculations were performed. The number of subjects is considered appropriate to evaluate the safety and efficacy of BMN 111 in the target population.		
Safety Analysis: All subjects who receive at least one dose of study treatment or who are randomized to the placebo-control group in this study will be included in the safety analysis. The safety analysis will be descriptive.		
All AEs will be coded using the most current version of Medical Dictionary for Regulatory Activities		

NAME OF COMPANY	SUMMARY TABLE	FOR NATIONAL AUTHORITY USE ONLY:
BioMarin Pharmaceutical Inc. [name]	Referring to Part of the Dossier: Volume: Page:	
NAME OF FINISHED PRODUCT: BMN 111		
NAME OF ACTIVE INGREDIENT: Modified rhCNP	Reference:	

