9.11.6.10 Anti- BMN 111 Immunogenicity Assessments and IgE Testing

Subjects randomized to receive BMN 111 or placebo will undergo immunogenicity testing. Blood (serum) samples for immunogenicity assessments will be collected at the time points indicated in the Schedule of Events (Table 9.1.1), and testing performed using validated assays. Neutralizing antibody (NAb) testing will be performed on Baseline and TAb positive samples drawn from subjects weighing ≥ 7.0 kg and waived for subjects < 7.0 kg.

Scheduled samples will be tested in one or more of the following assessments:

- Anti- BMN 111 total antibody (TAb)
- Anti-BMN 111 antibody cross-reactive with endogenous CNP, ANP, and BNP (TAb)
- Anti- BMN 111 NAb

Testing for the presence of cross-reactive antibodies that bind to endogenous CNP, ANP, or BNP and for the presence of BMN 111 NAb will be performed on baseline samples and anti- BMN 111 TAb-positive samples. Baseline NAb sample and cross-reactive TAb sample testing will be done at any time prior to the end of study.

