14.2 Safety Analysis

The safety analysis will be performed on safety population as defined in Section 14.7.2 and will be considered descriptive.

All AEs will be coded using the most current version of MedDRA will be used by the Sponsor to assign system organ class and preferred term classification to events and diseases, based on the original terms entered on the CRF.

All AEs will be coded using MedDRA. The incidence of AEs will be summarized by system organ class, preferred term, relationship to study treatment (as assessed by investigator), and severity. All AEs, including SAEs and AEs that lead to permanent discontinuation from the study and from the study treatment, will be listed. Hypersensitivity reactions and

symptomatic hypotension are of interest, and the percentage of subjects who report these AEs will be presented. Hypersensitivity reactions will be defined in the SAP.

Clinical laboratory data will be summarized by the type of laboratory test. For each clinical laboratory test, descriptive statistics will be provided on baseline as well as all subsequent visits.

All other safety measures including laboratory tests, vital signs, ECG, echocardiogram, hip clinical assessment, and concomitant medication data will also be summarized descriptively. Data summaries will be presented by treatment group (when applicable) for each cohort and overall. All safety results will be listed.

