NAME OF COMPANY BioMarin Pharmaceutical Inc. [name]	SUMMARY TABLE Referring to Part of the Dossier: Volume: Page:	FOR NATIONAL AUTHORITY USE ONLY:
NAME OF FINISHED PRODUCT: BMN 111		
NAME OF ACTIVE INGREDIENT: Modified rhCNP	Reference:	

STATISTICAL METHODS:

Sample Size Determination: Approximately 70 subjects age 0 to < 60 months at study entry will participate in this study. No formal sample size calculations were performed. The number of subjects is considered appropriate to evaluate the safety and efficacy of BMN 111 in the target population.

Safety Analysis: All subjects who receive at least one dose of study treatment or who are randomized to the placebo-control group in this study will be included in the safety analysis. The safety analysis will be descriptive.

All AEs will be coded using the most current version of Medical Dictionary for Regulatory Activities (MedDRA) to assign system organ class and preferred term classification to event and disease, based on the original terms entered on the eCRF. The incidence of AEs will be summarized by system organ class, preferred term, relationship to study treatment as assessed by the investigator, seriousness, and severity. All AEs, including SAEs and AEs that lead to permanent discontinuation from the study and from the study treatment, will be listed.

All other safety measures including laboratory tests, vital signs, ECG, echocardiogram, hip clinical assessment, and concomitant medication data will also be summarized descriptively. Data summaries will be presented by treatment group (when applicable) for each cohort and overall. All safety results will be listed.

Efficacy Analysis:

All randomized subjects who receive at least one dose of study treatment or placebo in the study will be included in the efficacy analysis.

Efficacy variables, including AGV (based on length/height) and length/height Z-score according to normal reference standards (not ACH), along with their change from baseline will be summarized by treatment group and cohort. Comparisons between treatment groups by cohort on these variables will be carried out where appropriate. Statistical comparisons will be considered descriptive. 95% CIs will be provided along with p values for treatment group comparisons.

Sentinel subjects will be summarized apart for both efficacy and safety.

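### Section 14.7.2 leaves the sentinel children out of the Safety Population while the Synopsis puts them in, and Sections 14.4 and 14.5 summarize PK and immunogenicity for randomized children only

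*Protocol*

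**What the plan says.** Protocol Section 14.2 fixes the set for the safety analysis: "The safety analysis will be performed on safety population as defined in Section 14.7.2 and will be considered descriptive". Section 14.7.2 defines that set as "All subjects who receive at least one dose of double-blinded BMN 111 or placebo in this study".

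The Synopsis, under Statistical Methods, gives a different rule, worded the same in the original and the amended protocol. The safety analysis includes "All subjects who receive at least one dose of study treatment or who are randomized to the placebo-control group in this study". It adds that "Sentinel subjects will be summarized apart for both efficacy and safety". That last sentence has no counterpart in Sections 14.2 or 14.7.2.

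On PK, Section 14.4 states: "For subjects randomized to BMN 111, PK parameters generated over the course of the study will be evaluated and summarized with descriptive statistical measures". Section 14.5 likewise summarizes immunogenicity in children randomized to BMN 111 or placebo, and Section 9.11.6.10 says that "Subjects randomized to receive BMN 111 or placebo will undergo immunogenicity testing". None of these sections mentions sentinels.

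Section 9.1 describes the sentinels as three children per cohort who receive BMN 111 before the rest of the cohort is randomized 1:1. More may be added.

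**The concern.** Every dosed sentinel gets BMN 111 and has no randomized, blinded assignment, so none can meet a condition that requires double-blinded drug. Taken with Section 14.2, this keeps sentinels out of the set on which safety is summarized by treatment group, by cohort and overall. The Synopsis puts them in.

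Safety and tolerability is a primary objective. Sentinels are the first children exposed in each age cohort. If the dose is adjusted under Section 9.1.1, the rest of that cohort starts at the adjusted dose, so the experience at that cohort's starting dose comes from the sentinels. Two statisticians working from different parts of this protocol would report different denominators, and possibly different incidences, for BMN 111.

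PK and immunogenicity are secondary objectives. Sentinel AUC is what triggers dose adjustment, yet the descriptive summaries planned in Section 14 do not name these children.

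**Working it through.** The protocol reports no formal sample size calculation, so the only figure of its own to reproduce is the head count.

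**Inputs.** Section 9.1 and the Synopsis of the amended protocol: 3 sentinels per cohort, plus at least 27, 17 and 17 children randomized 1:1 in Cohorts 1, 2 and 3. Section 14.6: approximately 70 children in total.

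**Step 1, head count.** (3 + 27) + (3 + 17) + (3 + 17) = 70, which agrees with the stated total. Of these, 9 are sentinels and 61 are randomized.

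**Step 2, sentinel share of BMN 111 exposure.** Share = sentinels / (sentinels + randomized / 2).

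| Case | Calculation | Share |
|---|---|---|
| All cohorts, minimum sizes | 9 / (9 + 30.5) = 9 / 39.5 | 22.8% |
| Whole-child rounding, larger active arms (14 + 9 + 9 = 32) | 9 / 41 | 22.0% |
| Whole-child rounding, smaller active arms (13 + 8 + 8 = 29) | 9 / 38 | 23.7% |
| Cohort 1 | 3 / (3 + 13.5) | 18.2% |
| Cohort 2, and Cohort 3 if its sentinels are dosed | 3 / (3 + 8.5) | 26.1% |
| Assumption: Cohort 3 sentinels only observed | 6 / (6 + 30.5) = 6 / 36.5 | 16.4% |
| Assumption: three further sentinels added | 12 / (12 + 30.5) = 12 / 42.5 | 28.2% |

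The 16.4% case is shown because the Synopsis describes the Cohort 3 sentinels as either under observation or receiving BMN 111. Section 9.1 says that they receive it.

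**Step 3, where a dosed sentinel is counted.**

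| Output | Section 14 | Synopsis |
|---|---|---|
| Safety analysis set | Out (14.2 with 14.7.2) | In |
| Separate sentinel safety summary | Not mentioned | Planned |
| PK summary | Not named (14.4) | No limit to randomized children |
| Immunogenicity summary | Not named (14.5) | No separate rule |

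**Step 4, effect on the pooled denominator.** If no case of an event is seen in n children, the one-sided 95% upper bound on its rate is 1 − 0.05^(1/n). For n = 30 this is 9.5%; for n = 39 it is 7.4%. This is the difference between the two table denominators, not an amount of data lost.

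**The case against.** The strongest reply is that sentinel safety data are already handled. The Synopsis plans a sentinel summary, Section 14.2 lists all AEs and safety results, the Sponsor reviews each cohort's sentinels after Day 8, and the DMC reviews them after 12 weeks of dosing. This stands.

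A reader might therefore infer too much from Section 14.7.2, namely that a sentinel event would go unseen. One could compute the chance of at least one case of a 5% event as 1 − 0.95^30 = 78.5% without sentinels and 1 − 0.95^39 = 86.5% with them, and call the gap lost detection. The documents do not support that: sentinel events would be observed and reported, and only their place in the pooled incidence is in doubt. The safety analysis is also descriptive, so no test or decision rule depends on that denominator.

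It can also be said that *double-blinded* is a leftover word. Section 14.7.1 opens with randomized subjects and Section 14.7.2 drops that qualifier, which suggests that a wider safety set was meant. That is plausible, but it supports correcting the word. No section calls the sentinels open-label; that they are unblinded is an inference from all dosed sentinels receiving BMN 111.

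On PK and immunogenicity, a reader might infer that sentinels are not sampled or their results not used. That does not hold either. The plasma sampling footnote to the amended Schedule of Events gives a specific rule for sentinels, Section 9.1.1 uses the mean sentinel AUC0-120, and the population PK model draws on available data from this study. What remains is narrower: the descriptive summaries in 14.4 and 14.5 name only randomized children.

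Finally, table layout is a matter for the SAP, which is not at hand. That covers the column arrangement but not the population definition, which the protocol has itself fixed in two ways.

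**Conclusion.** The concern holds as a contradiction between two stated definitions of the safety analysis set for a primary objective. Under Sections 14.2 and 14.7.2 the nine planned sentinels are outside the Safety Population; under the Synopsis they are inside it and are also shown separately. At the minimum cohort sizes they are about 23% of BMN 111-exposed children (22.0% to 23.7% by rounding), or about 16% if the Cohort 3 sentinels are only observed. The consequence is that they would be absent from the overall BMN 111 incidence under 14.7.2. It is not that their data would be lost. A smaller gap of the same kind exists in the PK and immunogenicity summaries.

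The shares assume 1:1 allocation at the minimum sizes and exactly three sentinels per cohort. Sections 14 and 9.11.6.10 can be read only in the original protocol. The amendment's summary of changes names no edit to them, but its detailed text revisions are not shown, so the current wording should be confirmed.

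**What to change.** - In Section 14.7.2, delete *double-blinded*, so that the Safety Population is all children who receive at least one dose of BMN 111 or placebo, and bring the Synopsis sentence into line with it.
- Keep the separate sentinel summary and state it in Section 14.2 as well as in the Synopsis.
- Add a column for all BMN 111-treated children, labelled as mixing sentinel and blinded exposure. Keep between-arm comparisons to randomized children.
- In Sections 14.4 and 14.5, and for consistency in 9.11.6.10, refer to children *treated with* rather than *randomized to* BMN 111 or placebo.

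The cost is a few wording changes and one table column, with no new data or visits. The drawback is that the pooled column combines two kinds of exposure, hence the label.

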15 DATA MONITORING COMMITTEE

In addition to safety and PK monitoring by BioMarin personnel, an independent DMC will act as an advisory body to BioMarin and will monitor the safety and PK of subjects in the study. After the sentinel subjects complete 12 weeks of dosing, a DMC review will occur to evaluate all available safety and PK data. Upon approval by the DMC, the next younger cohort will be opened and the 3 sentinel subjects will be enrolled.

The DMC will make recommendations for stopping or continuing the study on an individual subject level and/or on a cohort level per the pre-specified stopping criteria. Based on criteria outlined in the protocol, the DMC may also make endorsements for dose adjustments if needed.

Please see DMC Charter for further details.

16 COSTS, COMPENSATION, AND SUBJECT INJURY

There will be no charge to study subjects to be in this study. BioMarin will pay all costs of tests, procedures, and treatments that are part of this study. In addition, after IRB/IEC/REB approval, BioMarin may reimburse the reasonable cost of travel for study-related visits in accordance with BioMarin's study-specific travel and reimbursement policy. BioMarin will not pay for any hospitalizations, tests, or treatments for medical problems of any sort related solely to the study subject's disease. Costs associated with such hospitalizations, tests, and treatments should be billed and collected in the way that such costs are usually billed and collected outside the study.

The Investigator should contact BioMarin immediately upon notification that a study subject has been injured by the study drug or by procedures performed as part of the study.

Any subject who experiences a study-related injury should be instructed by the Investigator to seek immediate medical treatment at a pre-specified medical institution if possible, or at the closest medical treatment facility if necessary. The subject should be given the name of a person to contact to seek further information about, and assistance with, treatment for study-related injuries. The treating physician should bill the subject's health insurance company or other third party payer for the cost of this medical treatment. If the cost of the medical treatment is not covered by health insurance or another third party that usually pays these costs, then either BioMarin or the institution may pay for reasonable and necessary medical services to treat the injuries caused by the study drug or study procedures. In some jurisdictions, BioMarin is obligated by law to pay for study-related injuries without prior recourse to third party payer billing and/or regardless of fault. If this is the case, BioMarin will comply with the law.

17 CASE REPORT FORMS AND SOURCE DOCUMENTS

Electronic case report forms will be provided for each subject. The Investigator must review and electronically sign the completed eCRF casebook to verify its accuracy.

eCRFs must be completed using a validated web-based application. Study site personnel will be trained on the application and will enter the clinical data from source documentation. Unless explicitly allowed in the eCRF instructions, blank data fields are not acceptable.

In the event of an entry error, or if new information becomes available, the value will be corrected by deselecting the erroneous response and then selecting or entering the factual response. In compliance with 21 CFR Part 11, the system will require the personnel making the correction to enter a reason for changing the value. The documented audit trail will include the reason for the change, the original value, the new value, the time of the correction and the identity of the operator.

BioMarin's policy is that study data on the eCRFs must be verifiable to the source data, which necessitates access to all original recordings, laboratory reports, and subject records. In addition, all source data should be attributable (signed and dated). The Investigator must therefore agree to allow direct access to all source data. Subjects (or their legally authorized representative) must also allow access to their medical records, and subjects will be informed of this and will confirm their agreement when giving informed consent. If direct source document verification of study data by the site monitor is prohibited by institutional policy or local law, then the Investigator must make available facilities and/or personnel to allow GCP-compliant source verification to occur. Examples of such methods include certified copies of records which have study data visible but sensitive information redacted, or other GCP-compliant means agreed between the Investigator and the Sponsor.

A CRA designated by BioMarin will compare the eCRFs with the original source documents at the study site and evaluate them for completeness and accuracy before designating them as "Source Data Verified" (SDV). If an error is discovered at any time or a clarification is needed, the CRA, or designee, will create an electronic query on the associated field. Site personnel will then answer the query by either correcting the data or responding to the query. The CRA will then review the response and determine either to close the query or re-query the site if the response does not fully address the question. This process is repeated until all open queries have been answered and closed.

Before a subject's eCRF casebook can be locked, data fields must be source data verified and all queries closed. Refer to the Study Monitoring Plan for details on which fields must be

source data verified. The Investigator will then electronically sign the casebook, specifying that the information on the eCRFs is accurate and complete. The Data Manager, or designee, will then set the status of the forms, visits, and the entire casebook to Locked. Upon completion of the CSR, an electronic copy of each site's casebooks will be copied to a compact disk (CD) and sent to each site for retention with other study documents.

18 STUDY MONITORING AND AUDITING

Qualified individuals designated by BioMarin will monitor all aspects of the study according to GCP and standard operating procedures for compliance with applicable government regulations. The Investigator agrees to allow these monitors direct access to the clinical supplies, dispensing, and storage areas and to the clinical files, including original medical records, of the study subjects, and, if requested, agrees to assist the monitors. The Investigator and staff are responsible for being present or available for consultation during routinely scheduled site visits conducted by BioMarin or its designees.

Members of BioMarin's GCP Compliance Department or designees may conduct an audit of a clinical site at any time before, during, or after completion of the study. The Investigator will be informed if an audit is to take place and advised as to the scope of the audit. Representatives of the FDA or other Regulatory Agencies may also conduct an audit of the study. If informed of such an inspection, the Investigator should notify BioMarin immediately. The Investigator will ensure that the auditors have access to the clinical supplies, study site facilities, original source documentation, and all study files.

19 RETENTION OF RECORDS

The Investigator must retain all study records required by BioMarin and by the applicable regulations in a secure and safe facility. The Investigator must consult a BioMarin representative before disposal of any study records, and must notify BioMarin of any change in the location, disposition or custody of the study files. The Investigator /institution must take measures to prevent accidental or premature destruction of essential documents, that is, documents that individually and collectively permit evaluation of the conduct of a study and the quality of the data produced, including paper copies of study records (e.g., subject charts) as well as any original source documents that are electronic as required by applicable regulatory requirements.

All study records must be retained for at least 2 years after the last approval of a marketing application in the US or an ICH region and until (1) there are no pending or contemplated marketing applications in the U.S. or an ICH region or (2) at least 2 years have elapsed since the formal discontinuation of clinical development of the IP. The Investigator /institution should retain subject identifiers for at least 15 years after the completion or discontinuation of the study. Subject files and other source data must be kept for the maximum period of time permitted by the hospital, institution or private practice, but not less than 15 years.

These documents should be retained for a longer period, however, if required by the applicable regulatory requirements or by a BioMarin agreement. BioMarin must be notified and will assist with retention should Investigator /institution be unable to continue maintenance of subject files for the full 15 years. It is the responsibility of BioMarin to inform the Investigator /institution as to when these documents no longer need to be retained.

